#### **Quality assurance/monitoring**

Monitoring is performed by the Data and Safety Monitoring Board (DSMB). DSMB will review the safety, ethics, and outcomes of the study. It is independent from the sponsor and has no competing interests.

#### **Data management**

Data collection will be restricted to those who meet the eligibility criteria. Participants who withdraw from the study for any reason will be recorded in their medical records and reviewed by the trial monitor.

#### **Withdrawal and terminate from the study**

In case of unexpected harm to the patient, insufficient compliance, or withdrawal of informed consent, a patient will promptly be excluded from further study treatment. The reasons for withdrawal must be documented in the CRF.

#### **Handling of Missing Data**

All variables included in the CRF are mandatory. The method last visit carried forward will be used to handle the missing data.

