## **Design and Methods**

### **Trial design**

The RELAX study (ClinicalTrials.gov ID: NCT03017586) is a double blind, randomized, multicenter trial designed to evaluate the clinical effectiveness and safety of DBS using new device (G104, E202, L301/L302, PINS, Inc., Beijing, BJ, China) on patients with primary dystonia. Based on strict inclusion and exclusion criteria, patients with dystonia will undergo rigorous screening for the study. A total of five follow-up surveys have been arranged for the research. After recruitment, in the follow-up V2, participants will undertake the implantation of lead and IPG according to the target randomization. After the implantation, participants will be randomized (1:1) to one of two groups: the experimental group (EG) or the control group (CG). The IPG of participants in EG will be turned ON, the IPG of participants in CG will be turned OFF for 3 months. After 3 months of stimulation in the blinded conditions, unblinding, the IPG of participants will turn ON and receive follow-up assessments for another 3 months. The clinical measurements for the two groups include the Burke-Fahn-Marsden Dystonia Rating Scale (BFMDRS), the Short-Form General Health Survey (SF-36), the Beck Depression Inventory (BDI) et al. All outcomes will be calculated by blinded statisticians appointed by clinical research institute of Peking University following the end

of the trial. The protocol design is based on the guidelines of the Consolidated Standards of Reporting Trials (CONSORT) and Standard Protocol Items: Recommendations for Interventional Trials (SPIRIT), and the study results will also be reported according to these guidelines. Informed consent will be obtained from all participants in accordance with the policies of the board.

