### **Outcomes measures**

#### **Primary clinical outcomes**

The primary outcome measures will focus on the changes in movement scores on the Burke-Fahn-Marsden Dystonia Rating Scale (BFMDRS), which will be specifically assessed after three and six months of treatment.

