#### **Sample size and power calculations**

The study concerns the improvement of dystonia between EG and CG in terms of BFMDRS score in the 3 months follow-up. According to the results of study, which design is basically the same as this trial. With a power setting of 80% and calculations based on two-sided 95% confidence intervals, the study required 17 pairs for GPi and 14 pairs for STN. We assume that 10% of the trial participants will be lost to attrition. Thus, a total of 70 participants need to be allocated to each treatment group.

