#### **Statistical analysis**

All evaluations of effectiveness and safety will be conducted according to the intention-to-treat (ITT) principle. The final data will be analyzed using IBM SPSS 13.0 or higher (SPSS, Inc., Chicago, IL, USA) and SAS 9.4 or higher (SAS Institute Inc., Cary, NC, USA) software. A p-value < 0.05 will be considered statistically significant. Data will be analyzed with t-tests and  $\chi^2$  tests for continuous variables and categorical variables, respectively.

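### Carry-forward without a phase limit can enter a control patient's month-3 OFF score as the month-6 primary outcome (minor, cheap to fix)

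*Protocol*

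**What the plan says.** Five parts of the protocol bear on this.

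- **Handling of Missing Data:** "The method last visit carried forward will be used to handle the missing data". No phase, visit, group or endpoint is excepted.
- **Trial design:** after implantation, "the IPG of participants in CG will be turned OFF for 3 months", while EG is ON. After unblinding, "the IPG of participants will turn ON and receive follow-up assessments for another 3 months". The visits are counted but not itemised: "A total of five follow-up surveys have been arranged for the research".
- **Primary clinical outcomes:** the change in BFMDRS movement score, "which will be specifically assessed after three and six months of treatment".
- **Statistical analysis:** "All evaluations of effectiveness and safety will be conducted according to the intention-to-treat (ITT) principle". Continuous variables are compared by t-test.
- **Sample size and power calculations:** the trial is sized on EG against CG "in terms of BFMDRS score in the 3 months follow-up". On loss: "We assume that 10% of the trial participants will be lost to attrition".

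**The concern.** Carry-forward always assumes that nothing changes after the last observed visit. Here the protocol itself schedules a change between the source visit and the target visit. For CG, month 3 is the end of the OFF phase and month 6 is the end of the ON phase. A month-3 score carried to month 6 therefore comes from a different stimulation state from the one that month 6 is meant to describe. EG is ON in both phases and does not have this problem, so the rule treats two patients lost at the same time differently.

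At stake is the month-6 CG value, half of what the protocol calls its primary outcome for that group. It would understate the response to delayed stimulation. CG patients are expected under both targets, so the same values would also enter any month-6 comparison of GPi with STN, which the Discussion hopes to explore.

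**Working it through.** **1. The plan's own figure.** 17 pairs and 14 pairs give 2 × (17 + 14) = 62 patients. Inflating for 10% loss gives 62/0.9 = 68.9, so 69. By target, 34/0.9 gives 38 and 28/0.9 gives 32, total 70. The total of 70 reproduces. The pair counts cannot be checked, because no effect size or SD is given.

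**2. An illustrative ON-OFF effect.** This must be back-solved. Reading 17 pairs as 17 per arm (an assumption), a two-sided 5% t-test with 80% power implies D = 0.99 SD of change. The normal formula D = (1.960 + 0.842) × √(2/n) gives 0.96 for n = 17 and 1.06 for n = 14. If pairs meant a paired test, D would be 0.68 to 0.75.

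**3. The cross-phase error.** Let f be the share of CG whose last score is the month-3 visit, and let G be the CG gain from month 3 to month 6. The CG month-6 mean is understated by f × G. With mean OFF change zero and full catch-up, G = D = 0.99:

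- f = 5%: 0.05 × 0.99 = 0.05 SD, or 0.05 × 35 = 1.75 patients in expectation.
- f = 10%: 0.10 × 0.99 = 0.10 SD, or 0.10 × 35 = 3.5 patients.
- f = 0 (all loss before month 3): 0.

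**4. Sensitivity of that figure.**

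- Half catch-up: G = 0.495, giving 0.025 and 0.05 SD.
- CG improves by 0.2 SD while OFF, with the EG mean held at 0.99: G = 0.79, giving 0.04 and 0.08 SD.
- Paired reading, f = 10%: about 0.07 SD.
- Half of the late CG losses have an interim score at full ON effect: the step 3 figures halve.

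**5. If someone did compare EG with CG at month 6.** With equal loss in both groups, and baseline carried forward for patients lost before month 3, the net error is

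(late loss × G) − (early loss × true month-6 EG-CG difference).

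Loss before / after month 3:

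- Full catch-up (true difference 0): 5%/5% gives +0.05; 0%/10% gives +0.10; 10%/0% gives 0.00 SD.
- Half catch-up (true difference 0.495): 5%/5% gives 0.05 × 0.495 − 0.05 × 0.495 = 0.00; 0%/10% gives +0.05; 10%/0% gives −0.05 SD.

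Simulation with correlation 0.7 between visits agrees with these errors. At full catch-up with 35 per arm, the two-sided rejection rate is about 5.5% for 5%/5% and about 6.8% for 0%/10%, against a nominal 5%.

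**6. Month 3.** No OFF-to-ON switch precedes the month-3 score, so f × G does not enter that comparison.

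**7. Check of the remedy.** A repeated-measures maximum-likelihood model of the observed scores, run without a separate baseline covariate, gave a month-6 difference within 0.002 SD of the truth, with rejection of 4.6% to 4.7% at 19 per arm and 4.7% to 4.9% at 35 per arm. The baseline-adjusted form recommended below was not itself simulated.

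**The case against.** The strongest reply has five parts.

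- **No stated comparison is harmed.** The trial is sized on month 3, and both groups are ON afterwards. A reader might infer that the main EG-CG result is biased or its type I error inflated. The documents do not support that: the protocol states no month-6 EG-CG test, so the rejection rates in step 5 describe a hypothetical one. This stands. What remains is the CG month-6 value itself.
- **The loss timing is assumed.** The 10% attrition inflates a month-3 sample size and reads most naturally as loss by month 3, in which case this error is nil. This stands: the protocol gives no figure for later loss, so 5% and 10% are illustrations.
- **The OFF score is not wrong for everyone.** Under Withdrawal and terminate from the study, a withdrawn patient stops study treatment. A CG patient withdrawn at month 3 may never be ON, and an OFF score may then be closer to the truth than a modelled ON response. For an EG patient withdrawn in the same way, the carried ON score is the doubtful one. This stands, and it makes a sensitivity analysis necessary.
- **An interim ON score may exist.** The five visits are not itemised. Such a score would narrow the affected group, but anyone lost directly after month 3 would still be affected.
- **This is detail for the statistical analysis plan.** This part fails. The protocol did not leave the method open. It fixed one method for all missing data, and that method conflicts with its own delayed switch-on.

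**Conclusion.** The point holds, with minor harm. Followed as written, the rule enters an OFF score as the month-6 outcome for CG patients last seen at month 3, and nothing else in the protocol prevents it. For those who would have been stimulated, the CG month-6 response is understated by about 0.05 SD at 5% late loss and 0.10 SD at 10%, which is 5% to 10% of the assumed response. There is no error if all loss precedes month 3. The size rests on a back-solved effect of 0.99 SD, no mean OFF change, full catch-up and no interim ON score.

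A reader might also infer that the rule always favours EG. It does not: under half catch-up, baseline carry-forward for early losses can cancel or reverse the shift.

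**What to change.** In Handling of Missing Data:

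1. State that a score from the OFF phase is not carried into the ON phase.
2. Analyse month 6 with a baseline-adjusted repeated-measures model of the observed scores by group and visit. This keeps every randomised patient with at least one post-baseline score.
3. Require one sensitivity analysis: for withdrawals who receive no further stimulation, assume no ON benefit, in both groups alike.
4. If carry-forward is kept as a further sensitivity analysis, confine it to scores from the same phase. CG patients without an ON-phase score then stay missing at month 6 in that analysis.

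The cost is a few sentences and slightly more programming in SAS, which the protocol already names. No extra patients, visits or data are needed. The price is a missing-at-random assumption in the main model, which the analysis in item 3 tests for the patients where it is least plausible. The model may also be slightly conservative in small groups.

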#### **Secondary clinical outcomes**

Secondary outcome measures, including specific item scores on the Short-Form General Health Survey (SF-36), Visual Analog Scale (VAS), walking measurements, the Beck Depression Inventory (BDI), Mini-Mental State Examination (MMSE), and the rate of improvement of the BFMDRS score, were all observed and recorded at 3 and 6 months during the treatment period.

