#### **Safety outcomes**

The occurrence rate of adverse events (AEs)/serious adverse events (SAEs) are documented at the scheduled and unscheduled clinical visits will be used to evaluate the safety of DBS. The

investigators are responsible for the management of participants' AEs and SAEs. During assessments, the investigator will question the participants about the occurrence of AEs and record the information in the source documents and patient case report form (CRF). The clinician will turn off the DBS therapy and evaluate the vital signs of the participant if the SAE occurs, then the suited therapy would be given for the participant. The investigators may choose hospitalization, outpatient treatment, home visits, communication, or other follow-up methods. All incidents are reported to the regulatory authority. All safety-relevant events are promptly reported to the ethics committee and the safety monitor within 24 hours.

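### The protocol's single carry-forward rule has no outcome limit: it fills missing BDI and MMSE scores with values from an earlier treatment state, and has no valid meaning for adverse events

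*Protocol*

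**What the plan says.** All references are to the protocol.

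- **Handling of Missing Data** has two sentences. The first is "All variables included in the CRF are mandatory". The second is "The method last visit carried forward will be used to handle the missing data". No outcome is named and none is exempted.
- **Secondary clinical outcomes**, on the assessments of months 3 and 6, has: "the Beck Depression Inventory (BDI), Mini-Mental State Examination (MMSE), and the rate of improvement of the BFMDRS score, were all observed and recorded". BDI and MMSE are therefore secondary clinical outcomes, not safety outcomes.
- **Safety outcomes** has: "The occurrence rate of adverse events (AEs)/serious adverse events (SAEs) are documented at the scheduled and unscheduled clinical visits". These events are also entered in the CRF.
- **Statistical analysis** has: "All evaluations of effectiveness and safety will be conducted according to the intention-to-treat (ITT) principle". Continuous variables are compared with t-tests and categorical variables with chi-squared tests.
- **Trial design** and **Randomization and blinding**: baseline measurements come before target randomisation and implantation. Controls are off stimulation for 3 months, and then all patients are on for 3 months.
- **Withdrawal and terminate from the study** gives three grounds for ending study treatment: "In case of unexpected harm to the patient, insufficient compliance, or withdrawal of informed consent, a patient will promptly be excluded from further study treatment". Documentation of the reason in the CRF is required.

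**The concern.** The rule is a positive instruction, not a gap left for the SAP. An SAP that handled BDI, MMSE or adverse events differently would depart from the protocol.

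Carrying the last visit forward assumes that nothing changes after it. This design makes that assumption hard to defend, because the treatment state changes by plan between visits. Baseline is before surgery, month 3 is on or off stimulation by group, and month 6 is on stimulation for everyone. A carried value can therefore describe a patient in a different treatment state from the one being summarised.

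Two things are at stake for BDI and MMSE. Mood or cognitive change that occurs after the last visit does not reach the summary. The filled values also enter the t-tests as ordinary observations, so the stated precision is too high. Harm is one of the grounds for leaving study treatment, so missingness related to these outcomes is plausible, though not certain.

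Adverse events raise a different problem. They accumulate as dated occurrences rather than as a score repeated at each visit, so there is no earlier value that can properly stand in for a later one.

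**Working it through.** **Inputs.** Required pairs: 17 (GPi) and 14 (STN); attrition 10% (Sample size and power calculations). Total enrolment: 70 (Patient population and recruitment; Trial status). The sample-size section attaches the 70 to each treatment group; the total of 70 is used here. The protocol gives no event rate and no mean or SD for BDI or MMSE, so the values below that depend on them are assumptions.

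**1. The plan's own figure.** (17 + 14) × 2 = 62, and 62/0.9 = 68.9, so 69. By target, 34/0.9 = 37.8, so 38, and 28/0.9 = 31.1, so 32; the total is 70. The stated 70 is reproduced. Expected loss is 0.10 × 70 = 7, leaving 63.

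**2. What the rule inserts for BDI and MMSE.**

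| Time of loss | Value needed | Value inserted |
|---|---|---|
| Before month 3, either group | Month 3, after surgery | Baseline, before surgery |
| Months 3 to 6, stimulated group | Month 6, on | Month 3, on |
| Months 3 to 6, control group | Month 6, on | Month 3, off |

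This assumes that both scales are scored at baseline and then only at the two times listed. Because an MMSE below 24 is an exclusion criterion, a carried baseline MMSE is at least 24 for any correctly enrolled patient, whatever happened afterwards.

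**3. Size for the mean change.** Let d be the fraction lost, and let leavers truly change k times as much as completers. If all loss precedes month 3, the inserted change is zero, and

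reported/true = (1 − d) / [(1 − d) + d·k].

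With d = 0.10:
- k = 1: 0.9/1.0 = 0.90
- k = 2: 0.9/1.1 = 0.82
- k = 3: 0.9/1.2 = 0.75

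The attenuation applies to worsening and improvement alike. For loss between months 3 and 6, the error in the month-6 mean is d times the leavers' own change over those months. At d = 0.10 that is one tenth of it, and for controls that change includes the move from off to on.

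**4. Size for precision.** Counting 70 patients when 63 were observed multiplies the standard error by √(63/70) = 0.949 at an unchanged SD, about 5% too narrow. Inserting zeros also alters the SD. The variance of change becomes 0.9s² + 0.09μ², which is below s² whenever |μ| < 1.05s (√(0.10/0.09) = 1.05). Unless the mean change exceeds about one SD, 5% is therefore a lower bound.

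**5. Does carry-forward drive the adverse event rate?** Assume that 20% of the 63 completers have an event and that none is recorded for the 7 lost. Then 63 × 0.20 = 12.6, and 12.6/70 = 18%. If 20%, 50% or all of those lost had an event, the true rates are:
- (12.6 + 1.4)/70 = 20%
- (12.6 + 3.5)/70 = 23%
- (12.6 + 7)/70 = 28%

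The gap is 2 to 10 points. Deleting the carry-forward sentence leaves 12.6/70 unchanged. The gap comes from incomplete follow-up and the full intention-to-treat denominator, so it does not measure the effect of this rule.

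**The case against.** A reader might infer a stronger point: that patients lost before a harm is recorded are counted as unharmed for adverse events, mood and cognition. The documents do not support it.

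- **Adverse events.** The protocol says that CRF variables are mandatory; it does not say that each is imputed. Nowhere does it classify a lost patient as event-free. An event once recorded stays recorded. The 2 to 10 point gap arises with or without carry-forward, as step 5 shows.
- **Loss through harm.** The withdrawal section ends study treatment; it does not say that assessment ends. Reasons must be documented, the trial monitor reviews withdrawals, and safety-relevant events are reported within 24 hours. Loss caused by a known harm is therefore the kind most likely to be on record.
- **BDI and MMSE.** A decline already seen at month 3 is carried to month 6, not hidden. A purely as-observed month-6 summary would drop it.

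All of this stands. It removes any claim of a known understatement in the adverse event rate. It does not answer the narrower point: no sentence confines the rule, a documented reason for withdrawal does not supply the missing score, and classing BDI and MMSE as secondary outcomes leaves them within the rule. It may also be said that tabulation of events belongs in the SAP. That is fair for the layout of tables, but not for a rule that the protocol has already fixed.

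**Conclusion.** The point holds in a limited form. Followed as written, the rule replaces month-3 BDI and MMSE scores with pre-implantation values for early leavers. It replaces month-6 scores with month-3 values for later leavers, off stimulation in the case of controls. Change after the last visit is missed, and filled values are treated as data.

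The size is moderate: a mean change attenuated to about 82% to 90% of its true value, and standard errors about 5% too small or more. This rests on the protocol's 10% attrition, on all loss falling before month 3 (the least favourable timing for that comparison), and on leavers changing one to two times as much as completers. The direction is not fixed, since improvement is attenuated as well as worsening, and unequal loss between groups could bias the comparison either way.

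For adverse events the conclusion is only that the rule has no valid meaning there and should be stated not to apply. No numerical bias in the event rate is attributed to it. The correction is worth making because the sentence is binding and cheap to change. Whether carry-forward suits the BFMDRS is a separate question, not settled here.

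**What to change.** Amend Handling of Missing Data as follows.

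1. State that carry-forward does not apply to adverse events or serious adverse events. Count each once from the recorded events, and show the length of observed follow-up by group beside the counts.
2. Analyse BDI and MMSE from all observed visits without carry-forward, for example with a repeated-measures mixed model with group-by-visit means. This keeps a leaver's month-3 value, including any decline seen then, without inventing a month-6 value.
3. Report the number missing and the reasons for loss by group and visit. The mixed model assumes that loss is explained by the data observed. Where the reason given is harm, the reader needs to see it.

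The cost is protocol and SAP wording, a little more analysis work and slightly wider intervals. Follow-up length needs dates of last contact, which the protocol does not say are in the CRF; this should be confirmed. Visits, treatment and sample size are unaffected.

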#### **Data auditing**

This trial will be audited by the Research Ethics Committee and the China Food and Drug Administration. The audits will be performed when the first participant enrollment, half and all of the enrolled cases are completed.

#### **Discussion**

Dystonia is a movement disorder characterized by abnormal movements or postures. There are many different clinical manifestations and underlying causes. This potentially debilitating disease can cause various problems, leading to impaired health-related quality of life [8]. Deep brain stimulation (DBS) is a well-established surgical treatment for patients with dystonia refractory to medical

treatment including botulinum toxin injections [8-10]. Although DBS is a well-established treatment for dystonia, there is significant heterogeneity in treatment effect and few data are available to identify ideal surgical candidates [11]. It is widely understood that the GPi and STN have been two used targets in DBS surgery with robustly reduce the BFMDRS score. However, the optimal choice is still debate [12-14]. Additionally, its reported that the different subtypes of dystonia also contribute to the variation of DBS outcome [15-16].

This multicenter double-blind randomized clinical trial will enable us to evaluate the effect and potential side effects of DBS stimulation in patients with dystonia. We hope to exploring the relative effectiveness of different targets (GPi vs STN) after follow-up periods. This study has several strengths. First, group-assignment in the double-blinded phase was randomized. Second, we performed a power calculation for this study. Most important of all, this outcome might influence the target selection and patients who are candidates for DBS to treat dystonia.

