## Abstract

**Background:** Dystonia is a relatively rare group of movement disorders that often prove difficult to treat effectively. Nowadays, deep brain stimulation (DBS) has become widespread and established treatment for patients with dystonia. The bilateral stimulation of either the globus pallidus internus (GPi) or the subthalamic nucleus (STN) is effective and safe in improving clinical symptoms and quality of life for patients with dystonia. RELAX study is a multicenter, prospective, randomized study designed to evaluate the clinical effectiveness and safety of DBS in patients with dystonia.

**Methods/Design:** Participants will be recruited in approximately 10 centers across China. All patients will undergo genetic testing. Eligible participants with dystonia will undergo DBS implantation according to the target randomization. Then, participants will be randomized to one of two groups: the experimental group (EG) with DBS on or the control group (CG) with DBS off. The primary outcome measures will focus on the changes in the Burke-Fahn-Marsden Dystonia Rating Scale (BFMDRS) movement scores, specifically assessed at three and six months of treatment. Secondary outcome measures, including specific item scores on the Short-Form General Health Survey (SF-36), Visual Analog Scale (VAS), walking measurements, the Beck Depression Inventory (BDI), Mini-Mental State Examination (MMSE), and the rate of improvement of the BFMDRS score, were all observed and recorded at 3 and 6 months during the treatment period. The aim of this trial is to investigate the efficacy and safety of DBS in patients with primary dystonia and gain insight regarding the therapeutic effects of different targets. **Discussion:** This is a large sample, randomized controlled trial to comprehensively evaluate the effectiveness and safety of DBS in patients with dystonia of different target.

**Trial registration:** NCT03017586, clinicaltrials.gov, registered on January 11, 2017, <https://www.clinicaltrials.gov/ct2/show/NCT03017586>

**Keywords:** Dystonia, Deep brain stimulation, Subthalamic nucleus, Globus pallidus internus

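### Under the protocol's general rules, an exploratory GPi versus STN comparison at month 6 would use an unadjusted t-test and carry control patients' OFF scores into an ON time point; both are avoidable

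*Protocol*

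**What the plan says.** **Interest in the targets.** Target (GPi or STN) is assigned at random after baseline (Protocol, Randomization and blinding). The Abstract aims to "gain insight regarding the therapeutic effects of different targets". The Discussion adds "We hope to exploring the relative effectiveness of different targets (GPi vs STN) after follow-up periods" and ranks one consequence first: "Most important of all, this outcome might influence the target selection and patients who are candidates for DBS to treat dystonia".

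**Timing and stimulation state.** CG is off until month 3. All stimulators are then turned on for a further three months (Trial design). The primary outcome is change in BFMDRS movement score, "which will be specifically assessed after three and six months of treatment".

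**Sample size.** "The study concerns the improvement of dystonia between EG and CG in terms of BFMDRS score in the 3 months follow-up"; on that basis "the study required 17 pairs for GPi and 14 pairs for STN", and "We assume that 10% of the trial participants will be lost to attrition". The enrolment target is 70 (Patient population and recruitment; Trial status).

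**Analysis rules.** For continuous variables, "Data will be analyzed with t-tests" (Statistical analysis); no covariate is named. Missing values are replaced by the last visit, with no exception for the switch from off to on (Handling of Missing Data).

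**The concern.** If GPi and STN are to be compared with everyone stimulated, month 6 is the time to do it. Two of the protocol's general rules serve that comparison poorly.

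- **Precision.** A t-test on change uses the baseline score only by subtraction and ignores EG/CG assignment. Group matters at month 6, because EG has then had six months of stimulation and CG three. Both variables are already collected. In a trial of 70 patients, precision lost here cannot be bought back.
- **Carry-forward across the switch.** The last visit before month 6 is month 3, when CG is still off. A CG patient seen at month 3 who misses month 6 therefore contributes an unstimulated score to a comparison of stimulated patients. If losses are similar in both targets, a real difference shrinks. If CG losses are uneven between targets, a difference appears where none exists.

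**Working it through.** **Inputs from the protocol.** 17 pairs for GPi, 14 for STN, 80% power, two-sided 5%, 10% attrition, 70 patients.

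**Assumptions (the protocol gives no SD, effect size or correlation).** Differences are in SDs of BFMDRS change. The baseline-to-month-6 correlation r is 0.3-0.7. The ON-OFF effect is about 1 SD. All losses fall after month 3.

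**1. The protocol's own figure.** 17/0.9 = 18.9, so 19; 14/0.9 = 15.6, so 16. Then 2 × (19 + 16) = 70, which reproduces. Evaluable patients: 2 × 17 = 34 GPi and 2 × 14 = 28 STN, 62 in all. Read as two-sample t-tests, 17 and 14 per arm correspond to ON-OFF effects of 0.99 and 1.10 SD. This is the basis for assuming 1 SD.

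**2. Unadjusted t-test, GPi versus STN.** SE = √(1/34 + 1/28) = 0.255. With 60 df, the difference detectable with 80% power is 0.73 SD, power for 0.5 SD is 49%, and the 95% CI half-width is 0.51 SD.

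**3. Adjusted model.** Let k be the ratio of the month-6 SD to the baseline SD. The variance relative to a t-test on change is k²(1 − r²) / (1 + k² − 2rk), which is (1 + r)/2 when k = 1. With 58 df and k = 1:

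| r | Variance ratio | Power at 0.5 SD | CI half-width | Equivalent t-test n |
|---|---|---|---|---|
| 0.3 | 0.65 | 67% | 0.41 SD | 62/0.65 = 95 |
| 0.5 | 0.75 | 60% | 0.44 SD | 62/0.75 = 83 |
| 0.7 | 0.85 | 55% | 0.47 SD | 62/0.85 = 73 |

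The gain depends on equal SDs. At k = 0.8 and r = 0.3 the ratio is 0.5824/1.16 = 0.50, about double the effective sample size. At k = 1.4 and r = 0.7 it is 0.9996/1.00, no gain.

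**4. Carry-forward, losses even between targets.** A carried CG score is an OFF score and holds no target difference. Half the patients are CG, so at 10% loss 0.10 × 0.5 = 5% of the scores in each target are carried OFF scores. A true 0.5 SD becomes 0.5 × (1 − 0.05) = 0.475. Simulation gave 0.47-0.48. If only CG is lost, at 20%, the result is 0.5 × (1 − 0.10) = 0.45; simulation gave 0.45.

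**5. Carry-forward, losses uneven.** With 38 GPi and 32 STN patients and a 1 SD effect, each carried CG score moves its target's mean by 1/38 = 0.026 or 1/32 = 0.031 SD. Four CG losses in one target and none in the other give 4/38 = 0.105 or 4/32 = 0.125 SD when the true difference is zero. Simulated false differences were 0.10-0.13 SD, with type I error about 7-8% instead of 5%.

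**6. How likely is that imbalance?** With independent 10% loss in CG cells of 19 and 16, the chance of four or more losses in one and none in the other is about 3%; at 5% loss it is 0.8%.

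**7. Both changes together.** In simulation with 70 enrolled, a true 0.5 SD and 10% loss, the t-test with carry-forward had 47-48% power. The adjusted model on observed scores had 55-66% and averaged 0.50 SD. The losses were random within cells, so the near-absence of bias in the model is expected by construction.

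**The case against.** **The contrast is not in the protocol.** No section defines a month-6 GPi versus STN test or ties the t-test sentence to it. This stands. The contrast is inferred from the stated hope to explore targets after follow-up, the month-6 primary time point and the all-on design. The point is therefore about what the general rules would do to it.

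**Covariates belong in the statistical analysis plan.** Often so, and that plan is not shown. But the protocol does not leave the matter open: it names the test and the missing-data rule, and those are what is questioned.

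**The t-test is valid.** Agreed. Target is randomised, and without missing data its simulated type I error was at or below about 5%. The loss is of precision only, and its size rests on an unknown correlation and SD ratio.

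**The bias is small.** At the planned 10% attrition it is, unless CG losses are uneven, and the marked imbalance is unlikely. A patient lost before month 3 would carry no OFF month-3 score, so the figures are towards the upper end for a given total loss.

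**A stronger reading.** Because the Discussion ranks target selection so highly, just after citing a power calculation, a reader might infer that the protocol claims to be powered for GPi versus STN. It does not. The sample-size section limits itself to EG versus CG at three months within each target, and the Discussion's wording is exploratory.

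**Conclusion.** The point holds in a limited form. If GPi and STN are compared at month 6 under the protocol's general rules, the test is valid but usually less precise than it could be. Power for 0.5 SD is 49%, against about 55-67% with adjustment if r is 0.3-0.7 and the SDs are equal; with unequal SDs the gain runs from about nil to about double the effective sample size. Carry-forward also mixes OFF scores into an ON comparison. That follows directly from the text; only its size is assumed. A true 0.5 SD becomes about 0.47 at 10% loss, and a lopsided loss of about four CG patients creates a false 0.10-0.13 SD. This is modest but avoidable, and worth correcting because the change is nearly free. It does not make the target comparison invalid, and it leaves the powered EG versus CG comparison at month 3 untouched.

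**What to change.** **Statistical analysis.** State the target contrast: GPi minus STN in BFMDRS movement score at month 6, in all randomised patients, from a linear model with target, EG/CG group and baseline BFMDRS, reported as a difference with its 95% CI.

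**Handling of Missing Data.** For month 6, do not carry CG's OFF month-3 scores forward. Use a likelihood-based analysis of the observed scores. If months 3 and 6 are fitted jointly, include target-by-group-by-visit terms, so that CG's OFF scores at month 3 are not read as ON scores. Keep carry-forward as a sensitivity analysis.

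**Cost.** Text in two sections and one model; no new visits, patients or data. The likelihood analysis assumes missingness at random given the observed scores. The contrast stays exploratory, since even the adjusted model reaches only about 55-67% power for 0.5 SD under the equal-SD assumption. A caveat in the Discussion that GPi versus STN lies outside the power calculation would be optional wording, not part of this point.
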